2 STUDY OBJECTIVES AND ENDPOINTS

2.1 Study objectives

2.1.1 Primary objective(s)

The primary objective of this study is to assess the pharmacokinetics of MCI-186 after a single intravenous infusion of 30 mg over 60 min in subjects with mild or moderate renal impairment compared to subjects with normal renal function.

2.1.2 Secondary objectives

The secondary objective of this study is to investigate the safety and tolerability of MCI-186 in subjects with mild or moderate renal impairment and in subjects with normal renal function.

2.2 Study endpoints

2.2.1 Primary endpoint(s)

The following primary PK parameters of MCI-186 will be calculated in the study:

- Peak drug concentration (C_{max});
- Area under the concentration-time curve from time zero to the last quantifiable concentration ($AUC_{0\text{-last}}$);
- Area under the concentration-time curve from time zero to infinity ($AUC_{0\text{-}\infty}$);

2.2.2 Secondary endpoints

The following secondary endpoints will be evaluated during the study:

PK parameters of MCI-186

- Half-life ($t_{1/2}$);

2.2.3 Exploratory endpoints

Not applicable in the study.

3 STUDY DESIGN

3.1 Overall study design

This is a Phase I, open-label, single-dose study to evaluate the pharmacokinetics of MCI-186 in male or female subjects with mild renal impairment (Group 1, n = 11), moderate renal impairment (Group 2, n = 8) and normal renal function (Group 3, n=11) as defined using the estimation of glomerular filtration rate (eGFR) based on the 3-variable Japanese equation [7] at Day -1. Subjects may be replaced or additional subjects may be enrolled to ensure a minimum threshold of 6 completing and evaluable subjects per group. The sponsor adds three subjects with mild renal impairment and three subjects with normal renal function because PK data of three subjects in each with mild renal impairment and normal renal function will be excluded from PK analysis set. Therefore, each 11 subjects will be allocated in Group 1 and Group 3 respectively, 8 subjects will be allocated in Group 2 and at least 6 subjects will be completed and evaluable per group.

[figure not shown]
- Group 1: Subjects with mild renal impairment (eGFR 60-89 mL/min/1.73m² as determined by the 3-variable Japanese equation)
- Group 2: Subjects with moderate renal impairment (eGFR 30-59 mL/min/1.73m²)
- Group 3: Subjects with healthy normal renal function to match Group 1 and Group 2 for age, body weight, and gender (eGFR≥90 mL/min/1.73m²)

Order of Subject Enrollment

The control group (Group 3) will be enrolled once all renal impairment subjects (Group 1 and Group 2) will have been enrolled and will be matched with the renal impairment population with respect to age, gender and body weight. Age and body weight ranges must overlap between subjects with renal impairment and matched healthy subjects. After inclusion of all renal impaired subjects, the arithmetic mean and the 95% confidence interval of age and body weight at Day -1 will be determined. The group of healthy subjects will include subjects within the 95% confidence interval of the respective parameter. Each group to contain a minimum of 2 subjects per gender. If possible, mixed male and female groups, split approxmatory 50% across groups but with a minimum of two females per group (No analysis of the gender difference).

The subjects with mild renal impairment will be treated first. The second subject with mild renal impairment will not be treated until the completion of review for safety and PK profile in the first treated subject.

Three subjects with mild renal impairment will be treated, and then the investigator and the Sponsor will assess the safety and PK results in these three subjects until after the end of trial (Day 7). A safety and PK review will be performed by the Investigator and the Sponsor including the Medical advisor. The safety report will be compiled by the investigator, and the PK report will be compiled by . The Sponsor will calculate C_{max} and AUC for the three subjects, against predicted C_{max} and AUC. The investigator and the Sponsor will decide together if subjects with moderate renal impairment may be included. Progression to treatment of subjects with

moderate renal impairment (Group 2) will not occur until this safety and PK review has been performed and approval is recorded by the investigator and the Sponsor.

The first subjects with moderate renal impairment will be assessed the safety and PK profile by the Investigator and the Sponsor. The second subject with moderate renal impairment will not be treated until the completion of review for safety and PK profile in the first treated subject.

If there are significant safety concerns, the study may be stopped as described in Section 4.5.

Study Periods and Duration of Study

The study consists of

- A screening period (Day -21 to Day -2)
- A treatment hospitalization period (Day-1 to Day 3) with single intravenous infusion of 30 mg MCI-186 over 60 min on Day 1 and PK blood sampling until 48 hr post dose.
All subjects will be confined to the study center from Day -1 to Day 3. Safety assessments will be performed until discharge.
- A follow-up period (Day 7 +2 days)
An end of trial examination will be performed.

The duration of participation for the individual subject is expected to be up to 30 days.

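### Does selecting controls inside the 95% confidence interval of the impaired subjects' mean age and weight spoil the comparison with normal renal function?

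*Protocol*

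**What the plan says.** Protocol 3.1 (Order of Subject Enrollment) fixes the sequence: "The control group (Group 3) will be enrolled once all renal impairment subjects (Group 1 and Group 2) will have been enrolled", and Group 3 "will be matched with the renal impairment population with respect to age, gender and body weight". After the last impaired subject is included, "the arithmetic mean and the 95% confidence interval of age and body weight at Day -1 will be determined". The selection rule follows: "The group of healthy subjects will include subjects within the 95% confidence interval of the respective parameter".

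The same paragraph has a looser condition, "Age and body weight ranges must overlap between subjects with renal impairment and matched healthy subjects", and two on sex: "Each group to contain a minimum of 2 subjects per gender" and, if possible, groups "split approxmatory 50% across groups but with a minimum of two females per group".

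The band does not appear among the inclusion and exclusion criteria in Protocol 4.3 and 4.4. Protocol 3.1 also says that PK data from three mild and three normal subjects will be left out of the PK analysis set. SAP 7.7.1 rules out covariate adjustment, and the ANOVA in Protocol 10.3.5.1 and SAP 7.8.2 has renal group as its only factor. Balance in age and weight therefore depends entirely on how controls are chosen.

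**The concern.** A confidence interval for a mean describes how precisely the mean is known. It does not describe how far individuals spread, and it narrows as more subjects are enrolled. Used as an entry window, it would turn away most of the impaired subjects themselves. It is also far stricter than the neighbouring condition that ranges overlap.

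Three further worries follow.

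- **Sex.** A single band pooled over men and women lies between the two sexes. It favours lighter men and heavier women.
- **Variance.** Controls squeezed into a narrow band may vary less than the impaired subjects, while the ANOVA assumes a common variance.
- **Target.** The interval comes from all impaired subjects, including three mild subjects whose PK data will not be analysed.

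Group 3 is the denominator of both exposure ratios, the dose is a fixed 30 mg whatever the body weight, and as few as six subjects per group may be evaluable. A distorted reference group could not be repaired later.

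**Working it through.** The plan gives no band width, SD or expected pass rate, so there is no figure of its own to reproduce.

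**1. Width of the band.** Impaired subjects: 11 + 8 = 19 (Protocol 3.1). Half-width in SD units = t(0.975, 18)/√19 = 2.101/4.359 = 0.482. Without the three added mild subjects n = 16, and the half-width is 0.533.

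**2. Share of a like population inside.** Assuming normality, 2Φ(0.482) − 1 = 0.370 for one variable. For both, 0.370² = 0.137 if age and weight are independent, and up to 0.155 with a correlation of ±0.5. With n = 16 the shares are 0.406 and 0.165. If volunteers were distributed like the impaired subjects, finding 11 controls would take about 11/0.137 ≈ 80 candidates. The rule is strict.

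**3. Effect on the group mean.** If every control lies within mean ± 0.482 SD, so does the control mean. That holds whatever the age or weight profile of the volunteer pool. The overlap condition alone gives no such guarantee.

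**4. Sex.** The documents give no weights, so assume men 67 ± 10 kg and women 54 ± 8 kg in equal numbers.

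- Pooled mean: (67 + 54)/2 = 60.5 kg.
- Pooled SD: √[(10² + 8²)/2 + 6.5²] = √124.25 = 11.15 kg.
- Band: 60.5 ± 0.482 × 11.15, or 55.1 to 65.9 kg.
- Men inside: 34%, averaging 61.1 kg (−9% against impaired men).
- Women inside: 38%, averaging 59.6 kg (+10% against impaired women).
- Control mean with equal numbers: (61.1 + 59.6)/2 = 60.35 kg, which is 0.15 kg below target.

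Any other sex split among the controls gives an expected mean between 59.6 and 61.1 kg, within 0.9 kg of target. For assumed sex differences of 5–15 kg and within-sex SDs of 8–10 kg, 34–37% of each sex pass when the impaired pool is 50:50. In a pool that is 70–80% male, 38–43% of men and 17–36% of women pass. Women become harder to find, but two per group is not out of reach.

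**5. Variance.** A normal variable cut at ±0.482 SD has an SD of 0.274 of the original. If age and weight explain a share R² of the variance in log exposure, the control SD relative to the impaired SD is √(1 − R² + R² × 0.274²).

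| R² (assumed) | Control SD / impaired SD |
|---|---|
| 0.10 | 0.95 |
| 0.30 | 0.85 |

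For age, Protocol 1.3 points to a small share: PK parameters were much the same in elderly and younger men.

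**6. Interval coverage and a wider window.** A simulation took 8 evaluable subjects per group, assumed effects of age and weight on exposure, and a volunteer pool younger than the impaired subjects. Under the rule as written, controls were within about 0.5 year and 0.3 kg of the impaired mean, and the 90% interval covered 0.91. A wider individual window of ±10 years and ±20% of weight, with no check on the mean, left controls about 6.7 years younger and the intervals slightly wider.

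**7. The three mild subjects.** The mean of 19 differs from the mean of the other 16 by 3/19 = 0.16 of the gap between the three and the rest. Even a gap of a full SD moves the centre by only 0.16 SD.

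**The case for a change.** The strongest case for a change is that the text can be read in more than one way. It does not say whether the interval is for the mean or for individual values, whether it binds each control or the group, or whether it is pooled or by sex. A site faced with a volunteer just outside the band has two sentences pulling apart. Since matching is the only protection against imbalance in age and weight, one could argue that the rule should be exact.

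The ambiguity is real, but the readings differ mainly in recruitment effort. Applied per subject, the band keeps the control mean on target. Applied to the group, it sets the same requirement on the mean directly. If a 95% range of individual values was meant, about 95% of a like population passes on each variable and about 90% on both; this gives the weakest control of the mean, but it is ordinary matching. The band and the overlap condition are compatible, because controls near the centre of the impaired range necessarily overlap it. The band is also not an eligibility criterion, so the ban on waivers in Protocol 4, which concerns eligibility criteria, does not attach to it.

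Two smaller points stand. Within each sex, controls would be closer to the pooled mean weight than the impaired subjects are; no analysis by sex is planned, so this does not enter the reported ratios. And one control group serves two impaired groups, so it matches their pooled centre and not each one separately. That is the price of a shared control group, and a different window would not remove it.

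The enrolment order cannot be faulted on the evidence. The documents give no dosing dates for the three normal subjects whose data are excluded, and they may have entered after all impaired subjects then planned.

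**Conclusion.** No change follows. Read literally and per subject, the rule is a narrow window of ± 0.48 SD, met by about 37% of a like population on one variable and 14–16% on both. The cost falls on recruitment, and Protocol 4.2 draws controls from a volunteer database, where pre-selection by age and weight is plausible. In return the Group 3 mean is held close to the impaired mean, which is what an ANOVA without covariates relies on.

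A conflict with sex matching is not shown, and the unadjusted comparison is not biased: the weight shift is about 0.15 kg in the worked example. The loss of control variance is modest, and 90% interval coverage stays near nominal. These sizes rest on normality and on assumed weights and covariate effects that the documents do not supply. The bound on the control mean needs none of those assumptions.

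Loosening the window would ease recruitment but could worsen the match in means, a debatable exchange with no clear gain. The unstated details can be settled sensibly by the site and sponsor when controls are selected. The by-group summaries of age, sex and weight in Protocol 10.3.3 will show whether the match was achieved.

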3.2 Rationale for study design

This is a Phase I, open-label, single-dose study. Blinding will not be used because the primary endpoint, the assessment of specified pharmacokinetic parameters, is not subject to bias from the participants or observers.

Both males and females (with a minimum of two subjects per gender in each group) will be included into the study. A gender effect will not be investigated.

Renal function of the subjects, expressed as eGFR [mL/min/1.73m²], will be calculated based on the 3-variable Japanese equation.

The study design, including the chosen endpoints, follows the FDA and EMA recommendations for evaluating the effect of impaired renal function on pharmacokinetics. It is considered appropriate design for the clinical evaluation of the pharmacokinetics, safety, and tolerability of MCI-186 in this subpopulation of special interest.

3.2.1 Risk:benefit statement

1.7 million patients in AIS and 1500 patients in ALS in Japan have been treated with MCI-186 showing acceptable safety profile. While hepatic and renal disorders were reported in post-marketing in AIS, these events were not observed as clinically significant findings in AIS and ALS clinical trial. The package insert in Japan presents that MCI-186 is

contraindicated in patients with severe renal impairment and should be administrated with care in patients with hepatic impairment.

Therefore, as described in Section 1.4, severe renal impairment subjects as well as the following high risk subjects [5, 6] are excluded; subjects 1) who are advanced age (> 75 years) or 2) who present severe infection. In addition, the dosing regimen in this study is single dose of 30 mg MCI-186 intravenously administered over 60 minutes. 30 mg is one-half of the approved daily therapeutic dosage for treatment of AIS or ALS.

Furthermore, this protocol includes frequent assessment of clinical and laboratory parameters including BUN, creatinine, AST, ALT, LDH and CK, RBC count and platelet count. The study will be conducted in stepwise. Subjects with moderate renal impairment will only be included after the safety and PK are assessed in three subjects with mild renal impairment.

This is a PK study in healthy subjects and subjects with renal impairment. There are no direct benefits to the subject through participation in this study. However, they and other patients may benefit in future because the results of this study may guide appropriate use of MCI-186 ultimately in the drug labeling.

4 SELECTION AND WITHDRAWAL OF SUBJECTS

The Sponsor does not operate a Protocol waiver (i.e., approval for prospective protocol deviations) for eligibility criteria.

4.1 Number of subjects

A total of 30 subjects will be enrolled to ensure 24 subjects complete the study.

4.2 Recruitment methods

Subjects with renal impairment will be recruited from those patients already attending clinics for the treatment of renal function or may be identified from a review of relevant databases. Matched healthy subjects will be recruited from a database of volunteers at the study center or other sites. All recruitment material will be approved by the Institutional Review Board (IRB) prior to implementation.

4.3 Inclusion criteria

A subject will be eligible for enrolment in the study if ALL of the following criteria apply:

All subjects

1. Male or female subjects age 20 to 75 years (both inclusive) at signature of the Informed Consent Form (ICF).
2. Able to provide written informed consent to participate in this study after reading the ICF, and after having the opportunity to discuss the study with the Investigator or designee, before any screening or study related procedures take place.
3. In the Investigator's opinion, subject is able to understand the nature of the study and any risks involved in participation, and willing to cooperate and comply with the Protocol restrictions and requirements.
4. A body weight of ≥ 45 kg in males or ≥ 40 kg in females and a body mass index (BMI) ranging from 18 to 30 kg/m^2 (inclusive) at Screening and Day -1.

5. Female subjects

- a) who are postmenopausal (absence of menses for one year or more and follicle stimulating hormone (FSH) $>30 \text{ mIU/mL}$), or
- b) who are surgically sterilised, or
- c) who are congenital sterility, or
- d) who use an effective methods of birth control from the Screening or at least 2 weeks before Investigational Medicinal Product (IMP) administration (whichever is earlier) until 14 days after the last dose of IMP.

6. Male subjects (including those who have had a vasectomy)

- a) who agree to use an adequate contraception method (e.g., condom with spermicide or partner using effective contraception) and to not donate sperm until 14 days after the last dose of IMP.

Renal impaired subjects (in addition)

7. Subjects with mild renal impairment defined as eGFR 60-89 mL/min/1.73m² and subjects with moderate renal impairment defined as eGFR 30-59 mL/min/1.73m² as determined by the 3-variable Japanese equation obtained during Screening period (i.e., within 21 days before IMP administration) and Day -1.
8. Chronic and stable renal impairment defined as no clinically significant change in disease status at least 30 days before Screening, as documented by subject's recent medical history.

9. Acceptable clinical conditions in the opinion of the investigator on the basis of a physical examination, medical history, ECG, vital sign, and clinical laboratory test (biochemistry, haematology, coagulation and urinalysis) at Screening, Day -1 and pre-dose on Day 1. Subjects with stable mild chronic concurrent diseases, such as degenerative joint disease, controlled diabetes, hypertension or hyperlipidemia, etc. may be included.

Healthy subjects (in addition)

10. Subject with normal renal function defined as $eGFR \geq 90 \text{ mL/min/1.73m}^2$ as determined by the 3-variable Japanese equation at Screening and Day -1, and no evidence of renal damage including abnormalities in blood or urine test.
11. Good health and free from clinically significant illness or disease in the opinion of the investigator on the basis of a physical examination, medical history, ECG, vital sign, and clinical laboratory test (biochemistry, haematology, coagulation and urinalysis) at Screening, Day -1 and pre-dose on Day 1.

4.4 Exclusion criteria

A subject will NOT be eligible for this study if ANY of the following criteria apply:

All subjects

1. Presence or history of severe allergy to food, or any medicinal product or relevant excipient that is of clinical significance.
2. Subjects were previously administered MCI-186.
3. As a result of the medical screening process, the Investigator considers the subject not suitable for the study.
4. Clinically significant abnormal ECG findings at Screening, Day -1 or before dosing as in the opinion of the Investigator.
5. Any other history or condition (surgical or medical) of disease which will increase the risk to the subject or will affect PK of the study drug or will otherwise influence the assessments to be made in this study in the opinion of the Investigator.
6. Positive urine drug screen (if not due to concomitant medication) or alcohol test at Screening and Day -1
7. History of alcohol abuse or drug abuse
8. Subject regularly, or on average, drank more than 28 units (224 g as pure alcohol) for man or 21 units (168 g) for female of alcohol per week (e.g., 20 g is equivalent to 500 mL of beer, 22 g is equivalent to 180 mL of sake or 12 g is equivalent to 120 mL of wine)
9. Presence of active infection requiring antibiotics
10. Positive test for human immunodeficiency virus (HIV) antigen/antibody, hepatitis B surface antigen (HBsAg), or hepatitis C virus antibody (HCVAb)
11. Donate blood more than 200 mL within 4 weeks, 400 mL within 16 weeks for female or 12 weeks for male, 600 mL within 52 weeks for female or 1000 mL within 52 weeks for male, respectively before providing a signed ICF
12. Donate plasma or platelet component within 2 weeks before providing a signed ICF
13. Participation in another trial within 12 weeks or 5 times the half-life of the drug whichever is longer before providing a signed ICF. For biologics, the minimum period is at least 24 weeks or the period of the pharmacodynamic effect, or 10 times the half-life of the drug, whichever is longer before providing a signed ICF.
14. Subject is currently taking non-permitted concomitant medication. The subjects with normal renal function are restricted from use of any concomitant medications unless discussed and agreed with the Sponsor. On-demand use of acetylsalicylic acid for

mild analgesia or use of oral contraceptives is permitted. In subjects with renal insufficiency, the use of prescribed medications is permitted for renal or concomitant disease as described in Attachment 3.

15. Not willing to abstain from consumption of caffeine, cola or tea from admission to the unit (Day -1) to discharge the unit (Day 3).
16. Subjects have a current or history of hepatic disease (cirrhosis, hepatic cancer etc.) which might in the opinion of the Investigator influence study results.
17. Any condition associated with dehydration.
18. Female subjects
 - a) who have a positive pregnancy test at the Screening and on Day -1.
 - b) who are pregnant, lactating, or planning to become pregnant during the study.

Renal impairment subjects (in addition)

19. Acute renal failure
20. History of renal transplantation
21. Serum albumin <3.0 g/dL
22. Haemoglobin <8 g/dL.
23. Aspartate aminotransferase (AST) activity, or an alanine aminotransferase (ALT) activity of at least 3 times the upper limit of normal (ULN) range and, in the opinion of the Investigator, clinically relevant.
24. Uncontrolled, or untreated hypertension defined as a mean of 3 repeated measurements of systolic blood pressure (SBP)>180 mmHg and/or diastolic blood pressure (DBP)>110 mmHg.
25. Start of any new medication or new any changes to a current dosage within 4 weeks before IMP administration.

Healthy subjects (in addition)

26. History or presence of any renal disease
27. Uncontrolled, or untreated hypertension defined as a mean of 3 repeated measurements of systolic blood pressure (SBP)>160 mmHg and/or diastolic blood pressure (DBP)>100 mmHg.

